5.3.2.1. Analysis Methods

5.3.2.1.1. Primary Analysis

The primary efficacy analysis will be performed utilizing the hypothetical estimand defined above. The change from baseline in MADRS total score will be compared between the JNJ-55308942 mg once daily group and the placebo group at Week 6 in a mixed-effects model for repeated measures (MMRM), with time, intervention (placebo or JNJ-55308942), BD type (I or II), country, P2RX7 GoF SNP mutation genotype (homozygous or heterozygous), concomitant medication status (no mood stabilizer or antipsychotic, a mood stabilizer alone, an antipsychotic alone, or a combination of a mood stabilizer and an antipsychotic), and time-by-intervention interaction as factors, with baseline MADRS total score as a continuous covariate. Data after treatment discontinuation will be considered missing. The within-subject covariance between visits will be estimated via an unstructured variance-covariance matrix. In case of convergence problems, alternative variance-covariance structures will be attempted in the following order, with the first structure that converges being used in the analysis: heterogeneous Toeplitz, standard Toeplitz, and first order autoregressive. Kenward-Roger approximation will be used to estimate the denominator degrees of freedom. Sandwich estimator will be used to address the potential misspecification of the covariance matrix when a structured covariance matrix is used due to the convergence problem with the unstructured covariance matrix.

The comparison of JNJ-55308942 versus placebo will be performed using the appropriate contrasts directly from the MMRM analysis. A 2-sided 80% confidence interval (CI) for the difference in least squares means will be presented over time. A 1-sided p-value will be calculated at Week 6. Least square means of change from baseline (+/- SE) will be presented graphically over time.

Descriptive statistics of the actual values and the change from baseline to each postbaseline time point will be presented for MADRS total score by intervention group.

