9.1. Statistical Hypotheses

JNJ-55308942, compared to placebo, results in a significant improvement in the severity of the symptoms of depression in participants with BD in an MDE, as evaluated by change in MADRS total score from baseline at Week 6.

Hypotheses will be tested at 1-sided alpha 0.10. Multiplicity adjustment will not be carried out.

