9.4.1. Primary Endpoint(s)

Efficacy analyses will be based on the full analysis set.

The estimand for the primary efficacy analysis is defined with the following 5 attributes:

- Population: participants with BD types I or II and in an MDE.
- Endpoint: change from baseline in the MADRS total score at Week 6.
- Treatment: JNJ-55308942 [REDACTED] mg once-daily versus placebo.
- Population-level summary: the difference in mean change from baseline in MADRS total score at Week 6 between JNJ-55308942 [REDACTED] mg once-daily and placebo.
- Intervention events (ICE) and corresponding strategy: The ICE to be considered is discontinuation of study intervention. The ICE will be addressed with a hypothetical strategy, targeting the effect of the initially randomized treatment that would have been observed had all participants remained on their treatment throughout the double-blind treatment phase.

The primary efficacy analysis will be performed utilizing the hypothetical estimand defined above. The change from baseline in MADRS total score will be compared between the JNJ-55308942 [REDACTED] mg once-daily group and the placebo group at Week 6 in a mixed-effects model using repeated measures (MMRM), with time, treatment (placebo or JNJ-55308942), BD type (I or II), country, concomitant medication status (no mood stabilizer or antipsychotic, a mood stabilizer alone, an antipsychotic alone, a combination of a mood stabilizer and an antipsychotic), P2RX7 GoF SNP genotype (homozygous or heterozygous) and time-by-treatment interaction as factors, with baseline MADRS total score as a continuous covariate. Data after treatment discontinuation will be considered as missing. An unstructured variance-covariance matrix will be used. In case of convergence problems, alternative variance-covariance structures will be attempted in the following order, with the first structure that converges being used in the analysis: heterogeneous Toeplitz, standard Toeplitz, and first order autoregressive. Kenward-Roger approximation will be used to estimate the denominator degrees of freedom. Sandwich estimator will be used to address the potential misspecification of the covariance matrix when a structured covariance matrix is used due to the convergence problem with the unstructured covariance matrix. The comparison of JNJ-55308942 versus placebo will be performed using the appropriate contrast.

To support the primary efficacy analysis, 2 sensitivity analyses will be performed:

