3. SAMPLE SIZE DETERMINATION

The estimated sample size of 164 participants (82 participants per group) was determined based on the assumption of an effect size of at least 0.45 for the MADRS total score (difference in mean change from baseline at Week 6 between the JNJ-55308942 and placebo groups of 3.9 units with a standard deviation of 8.6). This is considered to be a clinically relevant difference in a population with BD types I and II. The standard deviation of 8.6 in the change in MADRS total score from baseline is a reasonable assumption based on data in a published phase 3 study of quetiapine in BD type I and type II depression (Calabrese 2005). Power is set at 90%, with a 1-sided alpha of 0.10 and a 6-week drop-out rate of 20%. The estimated number of completers to be included in the primary analysis is 132.

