5.3.2.1.2. Sensitivity Analysis

The primary analysis based on MMRM is valid and produces unbiased estimates of the treatment effect if missing data are missing at random (MAR), meaning that the probability of a value being missing, conditional on the observed data in the statistical model, is random and not dependent on the unknown value of missing data point. The MAR assumption cannot be verified vs. missing not at random (MNAR) using observed data. Therefore, a sensitivity analysis using copy-reference multiple imputation will be conducted under the MNAR assumption to evaluate the robustness of efficacy results and the effect of the missing data. In addition, a tipping-point analysis will be conducted if the primary analysis results show a significantly greater improvement in the MADRS

total score at Week 6 in JNJ-55308942 compared to placebo (i.e., 1-sided p-value \leq 0.1 in favor of JNJ-55308942).

The copy reference multiple imputation approach does not assume a sustained benefit of experimental intervention for the efficacy data that is either not used or missing after the intercurrent event and uses an imputation method that is based on the control group distribution and the estimated correlations between time points in the control group. MAR is assumed for intermediate missing data (i.e., missing data between non-missing observations). MNAR is assumed for monotone missing (i.e., missing data after the participant experienced an intercurrent event) in participants in the experimental intervention group, where efficacy scores are assumed as if the participant had always been in the control group. MAR is assumed for missing data in the control group.

This method will employ the following 3 steps:

Step 1 – Multiple imputation

If there are participants with a non-monotone missing data pattern, datasets with only monotone missing data patterns will be created first by imputing the intermediate missing values using the Markov Chain Monte Carlo (MCMC) method, which assumes a multivariate normal distribution over all variables included in the imputation model. This imputation will be done by intervention group. The variables to be used in the imputation are treatment, corresponding baseline values, and values observed at all double-blind visits (Weeks 1, 2, 4, 6). 50 imputations will be performed to create 50 datasets that now have monotone missing (i.e., missing data after the participant experienced an intercurrent event) data pattern.

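### The primary MMRM fits one baseline-MADRS slope across all visits; a baseline-by-time term would give a modest, assumption-dependent gain in Week 6 precision at very small cost

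*SAP*

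**What the plan says.** The primary model in SAP 5.3.2.1.1 has time-by-intervention as its only interaction and takes "baseline MADRS total score as a continuous covariate". Protocol 9.4.1 and the synopsis specify the same model: "time-by-treatment interaction as factors, with baseline MADRS total score as a continuous covariate". Time, treatment and the four stratification factors are main effects. No baseline-by-time term appears.

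On the residual side the model is fully flexible: "The within-subject covariance between visits will be estimated via an unstructured variance-covariance matrix". The post-baseline MADRS visits are Weeks 1, 2, 4 and 6 (SAP Table 2), and a p-value is planned at Week 6 only.

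The copy-reference and tipping-point analyses refit the same MMRM (SAP 5.3.2.1.2, Step 2). The MADRS subgroup models reuse it (5.4.1.2.2 and, when feasible, 5.4.2.7). PROMIS, PHQ-9 and GAD-7 use it with their own baseline scores (5.4.2.2 to 5.4.2.4). SHAPS is analysed by ANCOVA at Week 6 alone (5.4.1.1.2), so its baseline slope is specific to Week 6.

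**The concern.** For a change score, the baseline slope at visit t equals corr(baseline, score at t) × SD at t / SD at baseline − 1. A common slope is correct only if that product is the same at Weeks 1, 2, 4 and 6. The plan gives no reason to expect this.

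If the slopes differ, the model estimates a compromise slope and applies it at Week 6. Part of the Week 6 variance that baseline could explain then stays in the residual, and the primary standard error is larger than necessary. The primary endpoint also gets a less flexible baseline adjustment than SHAPS, a secondary endpoint. At stake is a small amount of precision that could be recovered from data already collected.

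**Working it through.** **1. The plan's own sample size.** Inputs from SAP section 3 and protocol 9.2: effect size 0.45 (difference 3.9, SD of change 8.6), 1-sided alpha 0.10, power 90%, drop-out 20%.

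- n per arm = 2 × (1.2816 + 1.2816)² / 0.45² = 13.14 / 0.2025 = 64.9, so 65.
- 65 / 0.80 = 81.25, so 82 per arm and 164 in total. This reproduces.
- 82 × 0.80 = 65.6, so 66 per arm and 132 completers. This reproduces.
- Power at 66 per arm with no baseline adjustment: 3.9 / (8.6 × √(2/66)) = 2.605; 2.605 − 1.282 = 1.324, giving 90.7%.

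The SD of 8.6 is that of the change itself, so the sample size takes no credit for baseline adjustment.

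**2. Formula for the loss.** Let b_t be the true slope at visit t and b_c the fitted common slope. Generalised least squares gives b_c = Σ w_t b_t, with weights w proportional to V⁻¹1, where V is the residual covariance across visits. Then

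Week 6 variance ratio (planned model / model with baseline-by-time) = 1 + (b_6 − b_c)² × SD_base² / (8.6² − b_6² × SD_base²).

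The standard-error (SE) ratio is its square root. The saving in completers is 132 × (1 − 1/variance ratio).

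**3. Assumptions.** The documents give none of the following: baseline SD (4 to 7 tried), slopes (linear in week between the Week 1 and Week 6 values), and the shape of V.

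**4. How V sets the common slope.** Baseline SD 5.5; slopes −0.15, −0.22, −0.36 and −0.50 at Weeks 1, 2, 4 and 6. CS is compound symmetry; AR is autoregressive.

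| Residual SD by visit (relative) and correlation | Weights, Weeks 1/2/4/6 | b_c | SE ratio | Completers |
|---|---|---|---|---|
| Strong rise 0.55/0.70/0.90/1; AR 0.85 per week | 1.15/−0.22/−0.04/0.12 | −0.167 | 1.025 | 6.3 |
| Mild rise 0.8/0.9/1/1; CS 0.6 | 0.55/0.27/0.09/0.09 | −0.22 | 1.018 | 4.6 |
| Constant; CS 0.6 | 0.25 each | −0.31 | 1.008 | 2.2 |
| Constant; AR 0.85 per week | 0.39/0.09/0.11/0.41 | −0.325 | 1.007 | 1.8 |

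First row in full: (0.500 − 0.167)² × 30.25 = 3.35; 73.96 − 0.25 × 30.25 = 66.40; 1 + 3.35/66.40 = 1.0505; √1.0505 = 1.025; 132 × (1 − 1/1.0505) = 6.3. Power at 66 per arm is 91.9% with the planned model and 92.9% with the added term.

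**5. Range over baseline SD 4 to 7 and all four covariance shapes.**

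| Slope, Week 1 to Week 6 | SE ratio |
|---|---|
| Equal (−0.3) | 1.000 |
| −0.10 to −0.20 | 1.000 to 1.003 |
| −0.15 to −0.50 | 1.004 to 1.043 |
| −0.10 to −0.70 (extreme) | 1.011 to 1.149 |

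A ratio of 1.043 means the SE falls by 1 − 1/1.043 = 4.1%, worth about 11 completers; it needs baseline SD 7 and strongly rising variance.

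**6. Simulation.** 1,500 trials per scenario, 82 per arm, 20% missing-at-random drop-out, unstructured MMRM with and without the term.

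- First-row case: empirical SE 1.445 against 1.407 (ratio 1.027); power 92.4% against 93.6%; mean estimate −3.86 under both models (truth −3.9).
- Equal slopes (−0.3): 1.450 without the term against 1.456 with it, a loss of about 0.4%, within simulation error.

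The simulation used maximum likelihood and a normal-type critical value, where the SAP specifies Kenward-Roger degrees of freedom. The comparison between models is therefore more reliable than the absolute power.

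**The case against.** The strongest case against is that nothing here is an error. The planned MMRM is prespecified and valid, the sample size does not lean on baseline adjustment, and the benefit of the extra term cannot be established from the documents because every input to it is assumed. All of that stands, and it limits the point to an optional refinement.

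Four stronger readings are tempting and are not supported:

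- *Week 6 is adjusted with roughly the Week 1 slope.* A reader might infer this from the way generalised least squares favours the least variable visit. It holds only if residual variance rises clearly over visits, which the documents do not report. With constant variance the common slope lies about midway (−0.31 to −0.325, between −0.15 and −0.50).
- *The Week 6 estimate is biased by baseline imbalance.* Under randomisation the issue is precision: the simulated estimates were the same under both models.
- *The trial is underpowered as a result.* The sample size uses the SD of the change, and the planned model already reaches 91.9% in the first-row case.
- *The term is free everywhere.* Three degrees of freedom applies to MADRS only, and the cost in small subgroup models has not been shown to be negligible. SAP 5.4.2.7 already fits the MMRM by concomitant-medication status and by country only when feasible.

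The objection does not remove the asymmetry: a loss of at most about 0.4% if slopes are equal, against a gain of up to about 4% in ordinary scenarios if they differ.

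**Conclusion.** The point holds as a minor, low-cost improvement. The primary MMRM imposes a single baseline slope on four visits although one visit carries the test, and the plan does not argue for the restriction. If slopes differ by visit, Week 6 is adjusted less efficiently than it could be.

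The size is conditional on the assumed baseline SD, visit slopes and visit covariances. The Week 6 standard error falls by 0% to about 4% in ordinary scenarios, worth nothing to about 6 completers at baseline SD 5.5 and up to about 11 at baseline SD 7. It falls by more only when slopes diverge very strongly. The planned analysis is valid as written.

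**What to change.** Before unblinding:

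- Add *baseline MADRS total score-by-time interaction* to the primary MMRM in SAP 5.3.2.1.1. The sensitivity analyses inherit it because they refit the same model. Cost: 3 degrees of freedom with about 132 completers.
- Record the change in SAP Appendix 2 (section 6.2), or align protocol 9.4.1. Protocol 10.3.1 requires a formal amendment for protocol changes, so the SAP entry is the lighter route.
- Add the matching baseline-by-time term to the full-sample PROMIS and PHQ-9 models (six post-baseline visits, 5 degrees of freedom) and the GAD-7 model (three visits, 2 degrees of freedom).
- In the MADRS subgroup models, include the term only where subgroup size makes it feasible, and state that condition in advance.

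No new data or visits are needed, and the sample size does not change. The SAP has already been revised once, so this is a few lines in a further version.

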5.3.2.1.2. Sensitivity Analysis

The primary analysis based on MMRM is valid and produces unbiased estimates of the treatment effect if missing data are missing at random (MAR), meaning that the probability of a value being missing, conditional on the observed data in the statistical model, is random and not dependent on the unknown value of missing data point. The MAR assumption cannot be verified vs. missing not at random (MNAR) using observed data. Therefore, a sensitivity analysis using copy-reference multiple imputation will be conducted under the MNAR assumption to evaluate the robustness of efficacy results and the effect of the missing data. In addition, a tipping-point analysis will be conducted if the primary analysis results show a significantly greater improvement in the MADRS

total score at Week 6 in JNJ-55308942 compared to placebo (i.e., 1-sided p-value \leq 0.1 in favor of JNJ-55308942).

The copy reference multiple imputation approach does not assume a sustained benefit of experimental intervention for the efficacy data that is either not used or missing after the intercurrent event and uses an imputation method that is based on the control group distribution and the estimated correlations between time points in the control group. MAR is assumed for intermediate missing data (i.e., missing data between non-missing observations). MNAR is assumed for monotone missing (i.e., missing data after the participant experienced an intercurrent event) in participants in the experimental intervention group, where efficacy scores are assumed as if the participant had always been in the control group. MAR is assumed for missing data in the control group.

This method will employ the following 3 steps:

Step 1 – Multiple imputation

If there are participants with a non-monotone missing data pattern, datasets with only monotone missing data patterns will be created first by imputing the intermediate missing values using the Markov Chain Monte Carlo (MCMC) method, which assumes a multivariate normal distribution over all variables included in the imputation model. This imputation will be done by intervention group. The variables to be used in the imputation are treatment, corresponding baseline values, and values observed at all double-blind visits (Weeks 1, 2, 4, 6). 50 imputations will be performed to create 50 datasets that now have monotone missing (i.e., missing data after the participant experienced an intercurrent event) data pattern.

The efficacy data that is either not used or missing after the intercurrent event at a given time point will be imputed using the imputation model of the control group, i.e., conditional on the data observed or imputed at previous time points relative to the mean of the model for the control group.

Step 2 – Analysis

The same MMRM analysis as described for the primary efficacy analysis will be performed for each of the adjusted fully imputed datasets.

Step 3 – Pooling

Rubin's methodology (Rubin 1987) will be applied to the MMRM results from the 50 imputed datasets to produce final inferences.

An additional sensitivity analysis using the delta adjustment multiple imputation (tipping-point) approach will be conducted if the results from the primary analysis show a significantly greater improvement in the MADRS total score at Week 6 in JNJ-55308942 compared to placebo (i.e., 1-sided p-value ≤ 0.1 in favor of JNJ-55308942). This approach imputes missing data over a range of possible scenarios for the treatment effect and finds a "tipping point" where the treatment effect in participants with missing data overturns the significant treatment effect. This method will

employ the same 3 steps as in the copy-reference multiple imputation sensitivity analysis except during the first step monotone missing data will first be imputed by MAR-based MI, and the imputed values in the experimental intervention group will be adjusted using a range of delta values to generate adjusted fully imputed datasets. The adjusted fully imputed datasets will be analyzed and combined using the same methods as Steps 2 and 3 of the copy-reference multiple imputation approach. The delta will be set in a range from 0 to Δ^* in increments of 1 as adding positive values results in higher (worse) scores. Δ^* represents the adjustments leading to the "tipping point". It is the smallest delta adjustment value at which conclusions change from favorable (i.e., statistically significant, 1-sided p-value ≤ 0.1 in favor of JNJ-55308942) to unfavorable. Between-group comparisons to placebo at Week 6 (e.g., 1-sided p-values, point estimates for intervention difference) will be displayed graphically for each considered delta, up to the "tipping point" adjustment. Clinical judgement will be applied to evaluate the plausibility of the assumptions underlying this "tipping point".

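### The sensitivity-analysis imputation steps name none of the four factors in the primary MMRM, so the estimate and tipping delta can be off in either direction if factor-related dropout differs by arm

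*SAP*

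**What the plan says.** - **Primary model (SAP 5.3.2.1.1).** Besides time, intervention, their interaction and baseline MADRS, the MMRM contains "BD type (I or II), country, P2RX7 GoF SNP mutation genotype (homozygous or heterozygous), concomitant medication status".
- **Meaning of MAR (SAP 5.3.2.1.2).** The SAP defines MAR relative to the observed data in the fitted model. For copy-reference it assumes MAR for intermediate gaps and for the control arm, and MNAR for data after the intercurrent event on active.
- **Step 1, intermediate gaps.** "The variables to be used in the imputation are treatment, corresponding baseline values, and values observed at all double-blind visits", that is Weeks 1, 2, 4 and 6. The sentence sits in the paragraph on MCMC imputation by intervention group.
- **Copy-reference, data after the event.** Values are imputed from the control-group model given earlier time points. No covariate list is given.
- **Tipping point.** "monotone missing data will first be imputed by MAR-based MI", after which delta is added to the imputed active-arm values in steps of 1. No covariate list is given.
- **Step 2.** Each completed dataset is analysed with the full primary MMRM, so all four factors return at that stage.

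No reason is given for the difference between the imputation and analysis covariates. Protocol 9.4.1 outlines the two sensitivity analyses without naming imputation covariates.

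**The concern.** A sensitivity analysis is easiest to read when it changes only the assumption under test. Because MAR is defined relative to the model, an imputation without BD type, country, genotype and medication status rests on a different MAR assumption from that of the primary MMRM. Suppose a factor predicts MADRS change and dropout depends on that factor differently in the two arms. Values imputed without it are then shifted by different amounts in each arm, and Step 2 adjustment cannot fully undo this. The distance to the tipping point then mixes the chosen delta with a covariate omission.

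Such a pattern is possible but not shown. SAP 5.3.2 says that a change or stop of background therapy leads to discontinuation of study intervention. That event can arise only in participants on background therapy, so missingness is tied to one of the four factors. Protocol 6.7 describes the drug as a weak inducer of one CYP enzyme and a moderate inhibitor of another, so tolerability with co-medication could differ between arms.

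**Working it through.** **1. The plan's own figures (SAP 3).** Inputs: "Power is set at 90%, with a 1-sided alpha of 0.10 and a 6-week drop-out rate of 20" per cent; "an effect size of at least 0.45 for the MADRS total score"; "placebo groups of 3.9 units with a standard deviation of 8.6".

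- Per arm: n = 2(z₀.₉₀ + z₀.₉₀)² / d² = 2 × (1.2816 + 1.2816)² / 0.45² = 64.9, so 65. Inflated: 65 / 0.80 = 81.25, so 82 per arm and 164 in total, as stated.
- Noncentral t with d = 0.45 and 66 per arm gives power 0.902. This matches "The estimated number of completers to be included in the primary analysis is 132".
- With 3.9/8.6 unrounded, n = 64 per arm and 160 randomised. The gap from 164 is rounding of the effect size.
- Expected without Week 6 data: 164 − 132 = 32, about 16 per arm.
- SE of the difference: 8.6 × √(2/66) = 1.50.

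**2. Conditioning sets side by side.**

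| Step | Assumption in SAP | Four factors named? |
|---|---|---|
| Primary MMRM | MAR | Yes |
| MCMC, intermediate gaps | MAR | No (explicit list) |
| Copy-reference, control arm | MAR | No (no list) |
| Copy-reference, active after event | MNAR by design | No (no list) |
| Tipping point, before delta | MAR | No (no list) |
| Step 2 MMRM | – | Yes |

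**3. Size of the effect.** Simulation with a true difference of 3.9 and about 20% monotone dropout. Imputation was by arm using sequential regression, with and without the factors. A Week 6 ANCOVA containing the factors stood in for the Step 2 MMRM. Assumed, not in the documents: the factors explain 5% or 15% of Week 6 variance, the visit correlations, and how dropout depends on the factors. Intermediate gaps were not simulated.

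Large-sample change in the Week 6 difference when the factors are left out (negative favours the drug; each cell gives 5% then 15% of variance):

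| Dropout pattern | MAR imputation | Copy-reference |
|---|---|---|
| Unrelated to factors | +0.01, 0.00 | −0.01, −0.04 |
| Related, same in both arms | +0.02, +0.01 | −0.02, −0.04 |
| Worse-prognosis strata, active only | −0.18, −0.32 | −0.18, −0.30 |
| Better-prognosis strata, active only | +0.21, +0.31 | +0.17, +0.23 |
| Opposite by arm, one way | −0.41, −0.66 | −0.34, −0.58 |
| Opposite by arm, other way | +0.42, +0.68 | +0.30, +0.51 |

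Mean tipping delta, 82 per arm, 200 trials per pattern, 20 imputations:

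| Dropout pattern | 5%: with → without | 15%: with → without |
|---|---|---|
| Unrelated | 11.7 → 11.9 | 11.0 → 11.0 |
| Same in both arms | 10.9 → 11.1 | 9.8 → 10.1 |
| Worse-prognosis, active only | 10.3 → 11.6 | 10.7 → 12.3 |
| Better-prognosis, active only | 10.4 → 9.6 | 10.7 → 9.1 |
| Opposite, one way | 10.5 → 12.5 | 10.4 → 13.6 |
| Opposite, other way | 10.3 → 8.7 | 10.3 → 7.6 |

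**4. Arithmetic check.** Delta applied to a missing fraction p of the active arm moves the mean difference by p × delta, so the tipping delta should move by about shift / p. At 15% of variance and p = 0.22: 0.32 / 0.22 = 1.5 (simulated 1.6) and 0.66 / 0.22 = 3.0 (simulated 3.2).

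**5. A separate run** used 400,000 per arm and one binary factor worth 2, 4 or 6 points (Monte Carlo error about 0.02). With dropout of 10%/30% by factor level on drug and 20%/20% on placebo, the estimate was 3.97 to 4.11 without the factor and 3.91 to 3.93 with it. Opposite patterns by arm gave up to 4.29. The same pattern in both arms gave no bias.

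**The case against.** **The list covers only the MCMC step.** This stands. Most missing data follow discontinuation, and for those steps the SAP is silent rather than explicit. For them the accurate charge is that no factor is named, not that the factors are expressly excluded. The covariates still need stating, and the only list available as a guide lacks the four factors.

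**Robustness will be overstated.** A reader might infer an error in the drug's favour. Neither the documents nor the simulation support that: mirror-image dropout patterns move the result against the drug by similar amounts. It is also not enough that dropout and outcome both depend on a factor. If that dependence is the same in both arms, the treatment difference barely moves.

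**Copy-reference is meant to depart from MAR.** This is correct for active-arm data after the event, so a different assumption there is no fault in itself. The point applies to the parts that the SAP calls MAR.

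**Delta = 0 would not match the primary anyway.** Also correct. MCMC is fitted by arm, while the MMRM has one baseline term and no baseline-by-time interaction, so neither model contains the other. Exact agreement should not be expected even after the fix.

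**The consequence is limited.** These are supportive analyses. The tipping point runs only after a significant primary result, Step 2 still adjusts for the factors, and earlier MADRS scores carry part of their information. All of this stands and limits the weight of the point.

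**Conclusion.** The point holds in limited form. As written, imputation that the SAP treats as MAR conditions on less than the primary MMRM does.

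The effect is negligible (at most 0.04 points) unless dropout depends on the factors differently by arm. If it does, the MAR-based Week 6 difference shifts by 0.18 to 0.68 points. That is 5% to 17% of the planned 3.9, or 12% to 45% of the SE of 1.50. The mean tipping delta moves by about 0.8 to 3.2 points, where the SAP's grid step is 1. The upper end needs opposite dropout patterns in the two arms. The sign cannot be known in advance.

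These sizes rest on assumed factor strength, correlations and dropout patterns; the documents give none of them. The copy-reference shifts also include active-arm data after the event, where the departure from MAR is intended, so they are illustrative only. The primary estimate, sample size, alpha and power do not change.

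**What to change.** In SAP 5.3.2.1.2:

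1. State the covariates of every imputation step: MCMC, copy-reference monotone and tipping-point monotone.
2. Include BD type, country, genotype and concomitant medication status, at least in the monotone regression steps. Add them as indicator variables in the MCMC step where feasible, keeping that step by arm.
3. Pre-specify how sparse country and medication levels are pooled for imputation.
4. Report the delta = 0 result beside the primary MMRM estimate, described as an approximate check.

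**Cost.** A few sentences of SAP text and slightly more programming, using factors already collected for randomisation. Pooling is needed because each arm has about 82 participants and MCMC assumes multivariate normality, which indicator variables satisfy only roughly. SAP 5.4.2.7 itself limits the MMRM by country and medication subgroup to cases where it is feasible. Pooling in the imputation but not in the MMRM leaves a small mismatch. In the simulation, standard errors without the factors were 0% to 4% smaller, so a slight loss of precision is also likely.
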